8.3 Recruit participants – Inpatients with SCI

- Once the MI trained PTs and OTs achieve basic MI competency, the experimental phase of the study will begin. The research assistants at both sites will approach a convenience sample of eligible inpatients that the PTs and OTs in the study are treating, for participation in the study. The research assistants will recruit and consent 10-11 inpatients for each of the therapists who were trained in MI as well as for each of the therapists who were not trained in MI for a total of 126 inpatients.

- The research assistants will ask the therapists when they feel comfortable to add another patient participant to their research caseload so as not to overburden the therapist with the research tasks. The patients will be kept blinded to whether their therapist has been trained in MI or not.

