1.1 Purpose

We plan to conduct a multi-site randomized controlled trial of motivational interviewing (MI) training for physical therapists (PTs) and occupational therapists (OTs) who treat people with SCI during inpatient rehabilitation. We will test whether patients treated by MI trained PTs and OTs demonstrate greater participation in therapy sessions and better functional, social, and educational/occupational outcomes relative to patients treated by therapists without MI training. This stage of research is appropriate because a Neilsen Foundation funded pilot study that we recently completed had promising results. Study results showed that SCI patients treated by MI trained PTs and OTs participated significantly more actively in therapy sessions compared to controls. However, the study had several limitations that need to be addressed to produce a more definitive and influential trial. First, the study was conducted at a single site and results may not generalize to other sites. Second, we did not examine whether MI training and improved participation resulted in patients having better clinically meaningful outcomes such as higher likelihood of discharge to home or superior functional, social, or educational/occupational outcomes. Third, therapists trained in MI achieved only minimal competency in MI skills. We hypothesize that if therapists received ongoing coaching to improve their MI

skills during the trial the positive impact on patient participation and other outcomes might be even more robust.

1.2 Project Aims:

1. To determine whether inpatients with SCI/D treated by PTs and OTs who receive MI training and coaching demonstrate greater therapy participation compared to those treated by therapists who do not receive MI training and coaching.
2. To determine whether inpatients with SCI/D treated by PTs and OTs who receive MI training and coaching demonstrate greater functional improvement at discharge from inpatient rehabilitation and greater community integration at 6 months after discharge compared to those treated by therapists who do not receive MI training and coaching.
3. To document an effect of training and coaching on MI skills and explore potential moderators and mediators of the effect of the intervention on therapy participation.

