- Willing to audio record conversations during regularly-scheduled rehabilitation therapy sessions with patients;

- Willing and able to participate in 16 hours of MI training; and
- Willing to receive feedback on MI skills.

Therapist exclusion criteria:

- Inability to speak and understand English
- Inpatient therapist specializing in spinal cord injury patients for less than 3 months; and
- Unwilling or unable to follow the study protocol

2.2 **Patients with SCI** will be recruited using participating therapists' caseloads and randomly selecting participants to be approached about participating in the study. When approached, patients will be read the patient recruitment script.

Patient Inclusion Criteria:

- Adults (18+)
- Presence of a traumatic or non-traumatic spinal cord injury
- Inpatient in the spinal cord injury unit of SRALab
- Has a physical or occupational therapist who is a participant in the study

Patient Exclusion Criteria:

- Inability to speak and understand English
- Cognitive deficits
- Unwilling to allow for therapy sessions to be recorded

3.0 Sample Size:

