4.3 Recruitment and screening of inpatients with SCI

A convenience sample of patients with SCI will be recruited based on new admissions to inpatient rehabilitation and the participation of their rehabilitation therapist in the study. The research team will approach patients assigned to one of the enrolled therapists at the time of their admission to an SRAlab inpatient SCI unit (on floor 21 or 22).

A research assistant will screen patients newly admitted to the 21 or 22 floor for presence of a traumatic or non-traumatic SCI via admission records in Cerner. Patients must be 18 years or older at time of admission and must speak English without a translator. Potential participants must also agree to having audio recordings of their therapy sessions.

The research team will communicate with the enrolled therapist to schedule a time before, during, or after rehabilitation sessions to recruit and screen patients. We will approach eligible patients using the recruitment script and flyer after assessing initial eligibility through medical records.

Interested patients will review the informed consent document with a member of the research team.

During the consent process, patients must agree to audio recordings of their therapy sessions—they will be informed that the audio recordings focus on the therapist and not the patient, but both sides of the conversation are needed to provide context to the therapist’s verbiage. We will instruct therapists to avoid using patients’ full names when recording therapy sessions. Audio recordings will be uploaded to Shirley Ryan AbilityLab OneDrive with limited permissions to maintain privacy of therapists and patients.

5.0 Research Locations:

This protocol describes research activities that will take place at Shirley Ryan AbilityLab under review of the Northwestern IRB. Therapy sessions will be held and recorded in the usual SCI rehabilitation units on the 21 or 22 floor. Research documents will be saved on the secure SRAlab network using SRAlab-approved devices. The research team will use REDCap to collect survey data and otherwise store participant information in password-protected files on the SRAlab server.

An identical protocol will be conducted at Baylor Scott White in Texas which will be reviewed under their local IRB. Any information that the SRAlab research team must share with the Baylor research team will be stripped of direct patient identifiers, such as full name and address.

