15.0 Audio/Video Recording/Photography

Therapy sessions will be audio recorded 2 times per week on mobile audio recording devices. The research team led by [name] will provide the therapist participants with the devices after they are enrolled in the study. The recordings will be the length of the therapist's typical session, approximately one hour but up to two hours. The therapists will download the audio recordings to a secure file (Shirley Ryan AbilityLabMicrosoft Teams secure network). Then [name] and [name] will listen to a sample of the audio recordings and rate the therapists' competency in MI using the Motivational Interviewing Treatment Integrity skill coding system during the baseline and MI competency phase.

Audio recordings will be stored separately from participant identifiers and will be labeled with Subject ID #'s rather than names. Audio recordings will be uploaded to Shirley Ryan AbilityLab OneDrive with limited permissions to maintain privacy of therapists and patients.

Participants will be informed of audio recordings during the informed consent process and throughout their study participation period. Audio recordings will be deleted after completion of the data analysis period.

During the randomized control trial phase, one random recording per week per patient participant will be shared with the Motivational Interviewing Treatment Integrity coding lab who will rate the motivational interviewing skills of the therapists by listening to 20 minutes of the recording and rating the session using the MITI 4.2.1 rating scale. These scores will be used to provide feedback to the therapists on their MI skills and to guide coaching sessions of the therapists for their MI skills. Coaching sessions of the therapists will take place individually approximately monthly or more often as needed based on the MITI scores.

16.0 Potential Benefits of this Research:

16.1 Therapist participants will be trained in motivational interviewing, an evidence-based skill that requires at least 16 hours of training by a designated instructor. Therapists who are not randomly assigned to the MI group during the

study period will have the opportunity to be trained in MI after completion of the study period. CEU credits will be offered upon completion of the MI workshop.

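### Sections 2.2 and 4.3/8.3 give different rules for choosing patients, and nothing stops an unblinded therapist's pacing decision from being made once the next candidate is known

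*Protocol*

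**What the plan says.** **How patients are chosen.** Protocol 2.2 works from participating therapists' caseloads, "randomly selecting participants to be approached about participating in the study". Protocol 4.3 says: "A convenience sample of patients with SCI will be recruited based on new admissions to inpatient rehabilitation". Protocol 8.3 has the research assistants "approach a convenience sample of eligible inpatients that the PTs and OTs in the study are treating".

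**When they are approached.** Under 4.3 the research team will "approach patients assigned to one of the enrolled therapists at the time of their admission". Under 8.3: "The research assistants will ask the therapists when they feel comfortable to add another patient participant to their research caseload". The reason given is "so as not to overburden the therapist with the research tasks".

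**Who knows the arm.** Therapists are randomized (8.1) and trained (8.2), and experimental-phase patients are recruited only once the MI therapists reach basic competency (8.3). Section 10.1 accepts that therapists cannot be blinded. The concealment in 8.1 covers study staff who enrol participants or collect data. Section 10.1 blinds the data-collecting team to assignment.

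**What differs between arms in workload.** Section 15.0 says: "Coaching sessions of the therapists will take place individually approximately monthly or more often as needed based on the MITI scores". The aims in 1.2 define the control group as patients "compared to those treated by therapists who do not receive MI training and coaching" by setting the MI group against them, so coaching belongs to the MI arm.

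**The concern.** The trial randomizes therapists and then recruits their patients. In such a design, randomization balances therapists. It balances patients only if the way they enter is unaffected by the arm. Anyone who knows the arm and can influence which patients enter, or at what point in the stay, opens a route to selection after randomization.

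The text leaves that route open in two ways. The selection rule is stated in two incompatible forms, so staff at two sites that are meant to run an identical protocol (6.1) cannot tell which to follow. And the person who says when the next place opens is the unblinded therapist.

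What would be at stake is comparability of the arms on the participation outcome. PRPS is rated weekly over the four weeks of enrolment and averaged (8.4). In the pilot (21.0) scores rose over time, the arm difference was larger in the first one to two weeks, and scores had converged by week 4. If that pattern follows time since admission (an assumption, since 21.0 does not say from when weeks were counted), a later start in the stay could change both the level of the average and the contrast between arms. No PRPS rating before exposure to the study therapist is described.

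**Working it through.** The point rests mainly on text; the protocol states no figure for it.

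**1. Selection rule.** Section 2.2: random selection from caseloads. Section 4.3: convenience sample of new admissions. Section 8.3: convenience sample of patients under treatment. A random draw and a convenience sample cannot both describe the same step. This is a conflict.

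**2. Timing.** Section 4.3: at admission. Section 8.3: when the therapist is comfortable, among patients being treated. These can be read together: the therapist signals readiness, and that therapist's next new admission is approached on arrival. The text does not say so, and the words in 8.3 would also admit a patient part-way through the stay. This is an unstated link, not a contradiction.

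**3. Influence of the therapist.**
- Order of events: randomize (8.1), train (8.2), recruit patients (8.3).
- Knowledge: the therapist knows the arm (10.1) and is not among the staff covered by 8.1.
- Power: pace only. Section 8.3 does not let the therapist name a patient.
- Gap: no section says which patient is next once a therapist is ready, what happens to patients admitted while the therapist is not ready, or that readiness must be declared before a candidate is known. Section 4.3 has the team contact the therapist to schedule recruitment and screening, so the therapist may already know the candidate.

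**4. Weight of one therapist.** 126 patients / 12 therapists = 10.5 each, matching the stated 10-11. Per arm, 126 / 2 = 63. One therapist's recruitment pattern therefore shapes 10.5 / 63 = 17% of an arm. This is a share of the sample, not an estimate of bias.

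**5. Coaching load.** The recruiting window is assumed to be 36 to 52 weeks. The upper end is the approximate year in 8.5. The lower end takes off eight training blocks (8.2) held every two weeks, if these fall inside that year: 52 - 8 x 2 = 36. At one session a month, this is about 8 (36 / 52 x 12 = 8.3) to 12 sessions per MI therapist and none per control. Session length is not given.

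**6. Would a cap on concurrent research patients be workable?** Four-week places per therapist = cap x window / 4.

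| Cap | 36 weeks | 52 weeks | Needed |
|---|---|---|---|
| 1 | 9 | 13 | 10-11 |
| 2 | 18 | 26 | 10-11 |

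A cap of 1 falls short in the shorter window even with no gap between patients. A cap of 2 leaves room.

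**The case against.** The strongest reply is that the plan already has real safeguards. Research assistants, not therapists, screen and approach. Enrolling staff are kept from the allocation, data collectors are blinded, and every therapist has the same 10-11 target. Section 4.3 is the more specific passage on timing and is clear. A difference in pace alone shifts only calendar time. All of this stands, and it limits the point to a possibility. It does not remove the conflict over selection, and none of these safeguards governs the therapist's pacing decision.

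Three stronger readings are tempting, and the protocol does not support them.

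- **Therapists pick their patients.** Section 8.3 gives no such power. Section 9.0 does let the clinical team advise against approaching a patient, but on grounds of the patient's interest and not of study workload.
- **Pacing differs by arm because only MI therapists are coached.** The reason in 8.3 is research burden, and the recurring per-patient task of recording and uploading falls on all therapists. No section counts coaching as a research task or links it to caseload. It could make pacing differ; the text does not show that it does.
- **Most caseload places are not research patients, so there is wide room for selection.** The budgeted caseloads in 3.3 (six full time, three half time) give patient-weeks, and turning these into patients needs a length of stay that the protocol does not give. If stays of 4 to 8 weeks are assumed, 10.5 patients are from 10.5 / (6 x 52 / 4) = 13% to 10.5 / (6 x 36 / 8) = 39% of a full-time therapist's patients. For a half-time therapist the range is 10.5 / (3 x 52 / 4) = 27% to 10.5 / (3 x 36 / 8) = 78%. Exclusions and refusals, whose rates are not stated, would narrow the room further. No conclusion should rest on this.

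**Conclusion.** The conflict between 2.2 and 4.3/8.3 is certain and has to be resolved in the protocol, because a recruitment rule is not a matter for the analysis plan. The therapist's say over pacing, made with knowledge of the arm and with no rule for who comes next, leaves differential recruitment by arm possible. The text does not show that it will occur, and the size and direction of any bias cannot be estimated.

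The consequences are not equally serious. A difference in start point could be described and adjusted for, since days from admission should be recoverable from the admission and therapy records already used (4.3, 8.4). A difference in patient mix beyond the recorded covariates could not. The relation between 4.3 and 8.3 on timing needs one clarifying sentence, no more. Overall this should be changed because the remedy is cheap and closes a selection route that opens after randomization; it is not a demonstrated flaw in the comparison.

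**What to change.** - Put one rule in 2.2, 4.3 and 8.3: blinded research assistants approach eligible new admissions on each enrolled therapist's list, in consecutive or in random order. Choose one and delete the other wording.
- Add a sentence linking 8.3 to 4.3: when a therapist is ready, the next patient under that rule is approached at admission.
- Let a therapist pause for workload only before the next candidate is identified, under the same rule in both arms, and log each pause.
- Record, per therapist, the numbers eligible, deferred, approached and declined, and days from admission to enrolment. Report these by arm.
- A cap on concurrent research patients is optional. If used, it should be the same in both arms and at least 2.

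The cost is text edits in three sections, a simple log, and slightly less flexibility for therapists over their research workload. Participation stays voluntary and separate from their duties, as 11.4 requires, because pausing remains open to them.

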8.4 Data collection

- Patient participants will be asked demographic questions following informed consent, and the research assistant will enter answers via REDCap (see 'DemographicSurvey' under 'supporting documents). The research assistant will abstract available variables about patient demographics and SCI injury characteristics, such as diagnosis and injury level, from the medical record. The patient participant may fill out the demographic survey via REDCap themselves if they prefer – the research assistant will review the answers, confirm with medical records if available, and follow up with participants in-person to clarify as needed.
- A research assistant will complete the Pittsburgh Rehabilitation Participation Scale (PRPS) for each patient participant during one randomly selected therapy session each week throughout the 4 weeks the participant is enrolled in the study. These PRPS scores will be recorded through REDCap, averaged, and analyzed.
- A research assistant will extract demographic data for each patient from the electronic medical record as well as minutes of therapy for each day from the electronic medical record for each patient participant. Demographic data extracted from the medical records will include: age, sex, injury level and severity, traumatic vs non-traumatic, injury etiology, years of education, and marital status, at the start of participation.
- All therapists will audio record therapy sessions with their patients as many times a week as possible (at least 3 sessions). They will download the recordings to a secure site so that a weekly session can be randomly chosen to send for **Motivational Interviewing Treatment Integrity (MITI)** coding. The MITI provides a global rating on five concepts of motivational interviewing: evocation, collaboration, autonomy/support, direction, and empathy. The ratings are on a 5-point Likert scale from 1 (low) to 5 (high). An average rating of 3.5 in the five concepts is considered beginning proficiency. In addition, frequency counts of MI behaviors that are open-ended questions, simple and complex reflections and MI adherent behaviors are tallied. Summary scores of reflection to question ratio, percent open questions, percent complex reflections and percent MI adherent behavior are computed.

- A research assistant will administer the Spinal Cord Injury Functional Independence (SCI-FI) via interview within approximately one week of patient discharge from inpatient rehabilitation. A research assistant will administer the Participation Assessment with Recombined Tools-Objective (PART-O) to patient participants at 6 months post-discharge from inpatient rehabilitation. Scores will be recorded on a fillable PDF and then entered into REDCap.

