3.1 Local sample size

We expect to enroll 90 participants at SRALab: 6 occupational or physical therapists plus 84 of their patients with SCI (of which $n = 18$ patients will only be enrolled as audio-only test participants).

The recruitment breakdown and timeline is as follows:

- Recruitment phase 1: 6 occupational or physical therapists
- Recruitment phase 2: 12 patients with SCI, 2 patients per therapist, will be recruited as audio-only test participants to assess baseline motivational interviewing skills prior to therapist randomization and training.
- Recruitment phase 3: Half ($n = 3$) of the therapists at each site will be trained in MI, so we will recruit 6 additional patients (2 per MI-trained therapist) as audio-only test participants to assess MI competency during the initial MI training phase.
- Recruitment phase 4: We will recruit 60-66 patients with SCI—10-11 patients per enrolled therapist—for the experimental phase, which includes audio recording of therapy sessions plus two additional questionnaires.

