- Once the research team enrolls 6 physical therapists or occupational therapists, demographic information will be collected by the research assistant via REDCap survey (see 'DemographicSurvey' under 'supporting documents'). The therapist participant may fill out the demographic survey via REDCap themselves if they prefer – the research assistant will review the answers and follow up with participants in-person to clarify as needed..
- All therapists will audio record two therapy sessions with SCI/D patients wearing a digital recorder on their name badge lanyard or on their clothing. This will provide a baseline level of MI skills. Audio-only test patients will sign an authorization to have their therapy session recorded (see "EditedSRAlabAudioConsentForm"). We will not obtain full informed consent from the audio-only patients because their identities will not be recorded and they will not participate in the patient questionnaires described below. The test audio recordings obtained in steps 8.1 and 8.2 will be destroyed after therapists' motivational interviewing skills are assessed.
- After all baseline recordings are complete, the data manager will perform a central computer-generated randomization and then transmit treatment allocation to [name], the MI trainer, via secure email. [name] will then contact enrolled PTs and OTs at each site to set up training as indicated. Randomization will be stratified based on therapist type (PT vs.

OT). The allocation sequence will be concealed from any study staff involved in enrollment of participants or data collection via a restricted access database program.

- Half of the therapists will be assigned to the experimental Motivational Interviewing group, and the other half will be assigned to the control group.

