10.1 Randomization and blinding

Half of the therapists will be trained in motivational interviewing, and the other half will proceed with normal care. As such, therapist participants cannot be blinded to their group assignment. Therapists who are not assigned to the MI group will have the opportunity to complete the training after completion of the study intervention.

Group assignments will be randomized by the study investigator, but the rest of the research team participating in data collection will be blinded to MI assignments. The research assistants collecting data and observing therapy sessions will not be trained in MI to further prevent bias.

Patient participants will be blinded to their group assignment—the therapists will be instructed not to disclose whether they are using MI techniques during therapy sessions or not. Patient participants will be told the nature of the intervention during the informed consent process.

11.0 Consent Process:

- 11.1** Written, informed consent will be obtained for all participants in the study, including therapist participants (n = 6 local) and SCI participants (n = 66 local).
- 11.2** The informed consent process will take place at Shirely Ryan AbilityLab by IRB-approved team members.
- 11.3** The research member obtaining consent will explain the study to potential participants in-person and provide a hard copy of the consent document for review. Participants will be encouraged to read the full consent document and ask any questions prior to signing. Two copies of the consent form will be created for each enrolled participant—the original copy will be stored in locked filing cabinets on the study team unit, and the second copy will be provided to the participant for their personal records. Consent may also be obtained online via REDCap if the participant prefers this process to a hard copy.
- 11.4** Any potential patient participant may refuse to participate and this will not impact the care that they receive at SRALab. Similarly, therapists' participation in this research study is entirely voluntary and unrelated to their responsibilities as an employee of SRALab. They will be neither rewarded nor penalized for their activities related to the research study. Also, these activities should not impact their responsibility to perform their duties as an SRALab-employed therapist. Participants can also withdraw at any time by verbally stating that they do not wish to participate anymore.

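### The weekly PRPS session is not tied to the recruiting therapist, so a patient whose PT and OT are enrolled in opposite arms can be rated in an opposite-arm session, and no rule states that patient's arm

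*Protocol*

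**What the plan says.** **The outcome rule.** Protocol section 8.4 has a research assistant score the PRPS "during one randomly selected therapy session each week throughout the 4 weeks the participant is enrolled in the study". The weekly scores are then averaged and analysed. The rule names the observer and the frequency, but not the therapist who leads the session.

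**The link between patient and therapist.** The patient inclusion criteria in section 2.2 require only that the patient "Has a physical or occupational therapist who is a participant in the study". Section 3.1 plans "10-11 patients per enrolled therapist". Under section 8.3, staff ask each therapist "when they feel comfortable to add another patient participant to their research caseload".

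**The unit of randomisation.** Section 8.1 allocates individual therapists: "Randomization will be stratified based on therapist type (PT vs" OT), half to motivational interviewing (MI) and half to control. It does not pair a patient's PT with the same patient's OT.

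**The fidelity measure, for contrast.** In section 8.4, "All therapists will audio record therapy sessions with their patients as many times a week as possible", and in section 15.0, "one random recording per week per patient participant will be shared with the Motivational Interviewing Treatment Integrity coding lab". These recordings come from enrolled therapists by construction.

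**The concern.** Aim 1 (section 1.2) compares therapy participation between patients of MI-trained and untrained therapists, and the sample size in 3.3 rests on the pilot PRPS effect. The comparison needs two things for each patient: an arm, and ratings taken under that arm's condition. The protocol implies the first without stating it, and leaves the second to the draw.

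The exposed group is patients with two enrolled therapists in different arms. For them a random draw over study-therapist sessions can land on either condition. If MI raises participation mainly in the trained therapist's own sessions, these ratings make the arms look more alike.

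This is a data-collection rule, which the protocol itself sets. A later analysis plan can define the patient's arm, but it cannot change which session was watched. If the session leader was not recorded, it cannot identify the affected ratings either. Two sites apply the rule separately under their own IRBs (1.3, 6.1), so an unstated intention could also be carried out differently at each.

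**Working it through.** **1. Can the situation arise?** The sections, side by side:

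| Section | What it fixes | What it leaves open |
|---|---|---|
| 2.2 | One enrolled PT or OT is enough | Whether the other therapist is enrolled, and in which arm |
| 8.1 | Individual randomisation, stratified PT/OT | Any pairing of one patient's PT and OT |
| 3.1, 8.3 | 10 to 11 patients per therapist | A stated rule for the arm of a patient with two enrolled therapists |
| 8.4 | One random session a week for the PRPS | Who leads it |

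Nothing excludes opposite-arm pairs.

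**2. How common are opposite-arm pairs among enrolled pairs?** Section 4.1 aims for 3 PTs and 3 OTs at the Shirley Ryan AbilityLab, and 3.1 has 3 therapists per site trained. An odd number in each stratum forces a 2:1 split in one discipline and 1:2 in the other. Of 3 × 3 = 9 possible PT–OT pairs, 2 × 2 + 1 × 1 = 5 are opposite-arm and 4 are same-arm. Where both therapists are enrolled and pairing is haphazard, opposite arms are therefore slightly more likely than not. The documents do not say how many patients have both therapists enrolled.

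**3. The plan's own figure.** With d = 0.56, two-sided alpha 0.05 and 1:1 allocation (3.3), an exact two-sample t-test needs 51.03 per group for 80% power. Rounded up, that is 52 per group or 104 in total, as stated, with power 80.7%.

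**4. Illustration of the direction only.** Let f be the share of rated sessions led by an opposite-arm therapist, equal in both arms. MI-arm patients are then rated under MI in a share 1 − f of sessions and control patients in a share f. The contrast is (1 − f) − f = 1 − 2f, so the effective d = 0.56(1 − 2f).

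Let q be the share of ratings led by the patient's other enrolled therapist. With the 5-in-9 count, f = 5q/9 and d = 0.56(1 − 10q/9). At 52 per group:

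| q (assumed) | f = 5q/9 | Effective d | Power |
|---|---|---|---|
| 0 | 0 | 0.560 | 80.7% |
| 0.10 | 0.056 | 0.498 | 71.0% |
| 0.25 | 0.139 | 0.404 | 53.3% |

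The plan implies 126 × 4 = 504 ratings, so q = 0.10 is about 50 ratings led by the other therapist, of which 504 × 0.056 ≈ 28 would be opposite-arm.

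The table assumes that MI acts only in the trained therapist's own sessions, that 0.56 is free of such mixing, and that patients are independent, as the calculation in 3.3 treats them. Neither q nor f has a source in the documents.

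**The case against.** **The text probably means study-therapist sessions.** Section 8.3 speaks of a patient's therapist in the singular and of each therapist's research caseload. Sections 8.5 and 15.0 use therapy session for sessions that study therapists record. The contrast with the fidelity rule is also weak: therapists make those recordings, so that sentence has to name them, whereas an observer scores the PRPS. This largely stands. A reader might infer from the literal wording that many ratings will come from therapists outside the study; the context does not support that. It does not answer the case of two enrolled therapists in opposite arms.

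**Any PT or OT session is a fair sample of participation.** Aim 1 concerns therapy participation in general, and section 1.3 describes the problem across both therapies. This stands in part. Sampling all of the patient's therapy is a defensible target, but it would still need a stated arm for each patient and a record of who led each rated session.

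**The loss may be small or nil.** Section 1.3 links MI to intrinsic motivation and self-regulation, and Aim 2 expects effects at discharge and at six months, so benefit may carry over into other therapists' sessions. The pilot also randomised individual therapists (21.0), so its d of 0.56 may already contain the same mixing; if to the same degree, nothing further is lost. This stands. A reader might conclude that the trial is underpowered for this reason; the documents do not support that conclusion.

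**Conclusion.** The point holds as a gap in the outcome rule that should be fixed. Section 8.4 does not tie the PRPS session to the recruiting therapist. Sections 2.2 and 8.1 allow a patient's PT and OT to be enrolled in opposite arms. No section states that patient's arm or requires the session leader to be recorded. These conclusions rest on the text alone.

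The likely direction of the bias is toward no difference, provided MI works at least partly through the trained therapist's own sessions. Its size cannot be derived. The power figures above show what assumed shares would do under unfavourable conditions and are not estimates for this trial. If staff already observe only the recruiting therapist's sessions, there is no such bias in the ratings, and the change simply writes the practice down for both sites.

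**What to change.** In section 8.4:

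1. Define the index therapist as the enrolled therapist under whom the patient is recruited, fixed at consent. State that the patient's arm is that therapist's randomised arm.
2. Draw the weekly PRPS session at random from the index therapist's sessions. If the index therapist leads none that week, rate the covering session and flag it.
3. Record who led each rated session and whether the patient's other therapist (PT or OT) is enrolled. Whoever holds the allocation list can then identify opposite-arm pairs for a sensitivity analysis.

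**Cost.** Some wording and two data fields. Research assistants already observe the rated sessions, so no visit is added, and no patient is excluded. The blinding described in 10.1 ("The research assistants collecting data and observing therapy sessions will not be trained in MI to further prevent bias") is not affected, because noting a leader's identity needs no allocation information.

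**Downsides.** Raters have slightly less scheduling freedom, and the PRPS then describes participation in the index therapist's sessions, not in all of the patient's therapy.

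**What it does not do.** It keeps opposite-arm sessions out of the rating, apart from flagged covering sessions. It does not remove a patient's exposure to both arms, which comes from randomising individual therapists. The sensitivity analysis in item 3 is there to examine that.
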